Several strategies have been implemented in Mexico to promote the adoption of healthy habits in the school environment (Safdie, Jennings-Aburto and Lévesque, 2013; Barriguet Melendez *et al.*, 2014). However, gaps remain in policies and programs focused on the prevention and reduction of the high prevalence of overweight and obesity in Mexican children. As a result, in August 2019 was launched the School Health program in Mexico with the aim to promote correct nutrition, adequate hydration, and regular practice of physical activity in children attending to primary schools. In its first phase, this will be implemented in 58 schools in Mexico City from October 2019.

The comprehensive analysis of public policies facilitates programs success (Guti rrez, 2017). This study aim is to comprehensively analyse the design, implementation, results, and impact of the School Health program during the first phase of implementation using mixed methods. Based on the results derived from this analysis, a set of recommendations will be provided to improve the feasibility of scaling up the program at the national level.

2. Background

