In response to the alarming prevalence of obesity and inadequate compliance with international health recommendations, in 2019 the SEP in coordination with the SS, the Mexican Institute of Social Security (IMSS, for its abbreviation in Spanish), the Institute of Security and Social Services of State Workers (ISSSTE, for its abbreviation in Spanish), the National System for the Integral Development of the Family (DIF, for its abbreviation in Spanish) and the National Institute of Public Health (INSP, for its abbreviation in Spanish) developed the School Health:

Healthy and Active Schools program (Salud Escolar: Escuelas Saludables y Activas, in Spanish) through a series of intersectoral workgroups (Secretaria de Salud and Secretaría de Educacion Pública, 2019).

This program aims to modify the school environment to promote healthy habits. It consists of a series of activities grouped into three components: Correct diet, which consists of updating and monitoring compliance with the general guidelines for the sale and distribution of prepared and processed foods and beverages, the delivery of hot breakfasts, and the strengthening of curricular contents on food and health. Adequate hydration refers to ensure the availability and accessibility of fresh water and promote its consumption during the school day. Physical activity consists of increasing the quantity and quality of physical activity among the school community before, during, and after the school day (Secretaria de Salud and Secretaría de Educacion Pública, 2019).

The first phase of implementation will be in 58 schools in Mexico City during the 2019-2020 school year among approximately 20,000 schoolchildren. The following strategies will be carried out in these schools using an intersectoral form:

- Measurement of weight and height in schoolchildren by DIF staff.
- Supervision of food and beverages availability by SS supervisors, and supervision of drinking fountains availability by the Federal Commission for the Prevention of Health Risks (COFEPRIS for its abbreviation in Spanish).
- Behavior change campaign by SEP.
- Application of a food and health questionnaire by SS supervisors.
- Training for the community delivered by SEP.

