- Promotion of physical activity by conducting quality physical education sessions, implementing active recreation strategies and active breaks. The SEP will be responsible of these strategies by general teachers (active breaks) and physical education teachers (physical education classes).
- Promote healthy hydration by SEP.
- Validation of a health-promoting school by SS supervisors.
- Delivery of hot breakfasts by DIF.

During the second phase (August 2020-July 2021) the program will be scaled to 14 states in the country where there are regions among the highest levels of marginalization including: Chiapas, Veracruz, Guerrero, Oaxaca, Yucatán, Hidalgo, San Luis Potosí, Puebla, Quintana Roo, Nayarit, Durango, Chihuahua, Campeche and Michoacán (Secretaria de Salud and Secretaría de Educacion Pública, 2019).

²⁹ Finally, in a third phase (August 2021 - July 2022) the program will be scaled nationwide. The implementation of the program will be carried out through SEP teaching staff (Secretaria de Salud and Secretaría de Educacion Pública, 2019).

3. Conceptual and theoretical framework

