- To analyze the impact of the School Health Program on schoolchildren physical activity levels, water consumption, and fruit and vegetable consumption.

7. Materials and methods

A comprehensive analysis of the design, implementation, results, and impact of the School Health Program will be carried out, which will be implemented in 58 schools in Mexico City during the first phase of implementation from October 2020. This study includes a design analysis of the Health School program, a quasi-experimental study to evaluate the impact of School Health on the individual outcomes of interest in the program (correct hydration, healthy eating, and physical activity), as well as an evaluation of the implementation. This analysis will be developed through three methodological stages which are presented in Figure 6. In this protocol is presented the first stage of implementation of this analysis only.

[figure not shown]

Figure 6. Stages, measurements and instruments of the Comprehensive analysis of Salud Escolar program

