7.1. Design analysis

The design analysis of Salud Escolar will be conducted through a desk-review and semi-structured interviews (if necessary). The information derived from this analysis will (1) facilitate decision-making processes to improve the internal logistics of Salud Escolar, and (2) facilitate the understanding of how Salud Escolar may contribute to solve the target health problem.

Several meetings will be held between the research team and the technical team of Salud Escolar in order to define key aspects of the methodology, such as the documents to be reviewed and the key actors to interview (if necessary), as well as for the review, discussion, and socialization of the preliminary results. The analysis will be carried out from October to November 2019 through the following phases:

Desk-review

Administrative records, databases, documents and public documentation related to Salud Escolar will be gathered. Additional information or documents considered as relevant by Salud Escolar technical team will be included. An adaptation of CONEVAL's design evaluation Terms of Reference (TOR) will be used as an instrument to conduct the desk-review (Table 2). In addition, references from the United Nations Children's Fund (UNICEF) will be considered to include a gender perspective during the analysis (Table 3). This approach considers the differences in roles and responsibilities attributed to women and men, girls and boys (UNICEF South Asia, 2018).

Three main documents have been considered for the desk-review to answer the questions of CONEVAL's instrument (Table 2): 1) Document Salud Escolar: Escuelas Saludables y Activas, 2) Program diagnostic and supervision instruments, 3) results of other international school-based programs that have been successful in promoting healthy habits in children and adolescents. Additionally, the following documents could be considered as well:

- General guidelines for the sale and distribution of prepared and processed foods and beverages in the schools of the National Educational System (Diario Oficial de la Federación, 2015a).
- Official Mexican Standard NOM-251-SSA1-2009, Hygienic practices for the process of food, beverages or supplements (Diario Oficial de la Federación, 2015a).
- Official Mexican Standard NOM-043-SSA2-2005, Basic health services. Promotion and education for health in nutrition. Criteria for providing guidance (Diario Oficial de la Federación, 2005).

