7.3 Impact analysis (baseline measurement)

Considering that Salud Escolar aims at creating healthy school environments, the impact analysis will be focused on the evaluation of some individual and environmental indicators.

Study design

A quasi-experimental design with baseline and endline evaluation will be used in schools where the School Health Program will be implemented (intervention group), and in schools where the program will not be implemented (control group). Measurements will be made prior to the start of the school program (pre-intervention), and 10 months after its implementation (post-intervention).

Study hypothesis

Based on similar studies previously carried out in the school population (Carriedo *et al.*, 2013; Safdie, Jennings-Aburto and Lévesque, 2013; McKenzie, 2015), we hypothesized the following changes in the endline measurement among children exposed to Salud Escolar, in comparison with those in the comparison group (not exposed to the intervention program):

- water consumption will increase by 171 ml (Carriedo *et al.*, 2013),
- time engaged in MVPA will increase in total 10 minutes per day, with an increase of 4 minutes per day during school recess and 4 minutes per day during physical education classes (Haerens *et al.*, 2007),
- the percentage of girls/boys who consume fruits and vegetables daily in the school environment will increase by 6.7% (Safdie, Jennings-Aburto and Lévesque, 2013).

Sample size calculation

The impact analysis study will be carried out in 30 primary schools in Mexico City (Intervention group = 15; Control Group = 15). The number of schools included was defined to better identify the effect (with a small number of schools the effect of the intervention could be confused with the characteristics of the schools) (Soto-Estrada *et al.*, 2016). Other criteria considered were the short time available for data collection (no more than three months according to reports by the Ministry of Health based on their experience during the implementation of the Health in your School program), as well as the available funds.

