7.4 Implementation analysis (**Second stage**)

An analysis of the implementation of the first phase of Salud Escolar will be carried out approximately 6 months after the program begins. The study will be cross-sectional and mixed methods will be used. The application of both approaches (i.e. qualitative and quantitative) for the analysis of health programs is favorable to understand different aspects of the implementation process (Jones *et al.*, 2010). This analysis will be carried out in the months of January and April 2020, through the phases described below.

Quantitative component Information gathering

It will take place in the 58 schools selected for the implementation of the first phase of the Program. A checklist designed by the SS will be used to verify compliance with the General Guidelines for the Sale and Distribution of food and beverages prepared and processed in the schools of the National Educational System and the General Guidelines for the installation and maintenance of drinking fountains in the schools of the National Educational System. This instrument will be applied simultaneously by the INSP research team and the SS as follows: 1) verify that the processes are being carried out as established in the Guidelines, and 2) analyze the validity of the instrument.

Field operative

For the instrument validity eight firework teams of two members each will apply the checklist in the 58 schools on two different times (at least 15 days apart), each checklist is estimated to take 60 min. This information will be captured at the time of visiting the schools on the REDCap platform.

Analysis of the information

The statistical package STATA 2015 will be used to conduct a descriptive analysis using means \pm standard deviation for continuous variables and n (%) for categorical variables.

Qualitative component

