8.2. Impact analysis

Parents written consent will be requested for the application of the sociodemographic questionnaire, and for the authorization of the collaboration of their children in the following activities: 1) diet questionnaire, 2) hydration questionnaire, 3) accelerometry. Likewise, the consent of the schoolchildren will be requested. For the application of the School Audit in the intervention and control schools, the written consent of the schools' principals will be requested. Each participant will be assigned a unique ID.

The information obtained as part of this research will be kept confidential and will be known by the evaluation team only. All field records will be kept in the principal investigator's office, with restricted access for people who are not involved in the project. The audio files will be deleted once completed data transcription and analysis.

Since the study will not handle human samples, it does not imply biosecurity risks. Regarding the ethical aspects, we consider that the proposal involves minimal risks for the participants since, the ethical principles of the field research will be respected including informed consent, autonomy and freedom to participate or not in the project.

9. Expected results

Knowledge gained from this comprehensive analysis will facilitate the development of further recommendations and strategies to support evidence-based decision-making processes towards the nationwide upscaling of Salud Escolar. These recommendations will be based on the gender perspective grounds. In addition, it will be possible to compare strategies included in Salud Escolar against evidence-based interventions for the prevention and control of childhood overweight and obesity. Results from this study will allow to establish a baseline evidence on the knowledge, attitudes, and practices of schoolchildren attending to public primary schools in Mexico City regarding correct nutrition, adequate hydration, and physical activity. This study will provide an up-to-date data of the schoolchildren physical activity and diet to subsequently analyze the results and impact of Salud Escolar.

10. Timeline

The timeline for the general project is presented in Figure 6. For Stage 1, two weeks of training and two and a half months for gathering information are considered.

11. Funds and deliverables

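### Read literally, the ten-month endline falls in August, after the phase 1 school year, when 6th graders would have left and could give no data collected at the study schools

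*Combined protocol and SAP*

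**What the plan says.** All references are to the combined protocol and SAP.

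- **Endline rule.** Section 7.3, Study design: "Measurements will be made prior to the start of the school program (pre-intervention), and 10 months after its implementation (post-intervention".
- **Programme start.** The introduction says "In its first phase, this will be implemented in 58 schools in Mexico City from October 2019", and also dates the programme's launch to August 2019. Section 2.3 places phase 1 "in 58 schools in Mexico City during the 2019-2020 school year". The opening of section 7 gives a different year: "implemented in 58 schools in Mexico City during the first phase of implementation from October 2020".
- **Other dated activities.** These fit 2019. For the design analysis (section 7.1): "The analysis will be carried out from October to November 2019 through the following phases". For the implementation analysis (section 7.4): "This analysis will be carried out in the months of January and April 2020".
- **Next phase.** Section 2.3: "During the second phase (August 2020-July 2021) the program will be scaled to 14 states in the country". Phase 3 follows on the same August-to-July cycle one year later.
- **Timeline.** Section 10: "The timeline for the general project is presented in Figure 6". That figure is not shown in the text available here.
- **Who is measured.** Section 7.3 samples children from 1st to 6th grade. It sizes the study as a followed cohort, with a baseline-to-endline correlation of 0.2 and a 20% allowance for loss. Research question 4 (section 4) names 3rd to 6th grade.
- **Fruit and vegetable outcome.** This has the largest sample size in Table 6 (388). The hypothesis in section 7.3 confines it to consumption at school. Under Measurements, food is weighed at recess, but a 24-hour recall given by the caregiver, with the child reporting food eaten at school, is also assigned to fruit and vegetable consumption.

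**The concern.** An endline defined only by months elapsed can cross a school-year boundary, and this one does on either stated October start. Taking 6th grade as the last primary year, children in that grade at baseline would no longer attend the study schools in August. Whatever must be observed at the school could not be collected from them: food weighed at recess, and activity observed in PE and recess where the same children are followed.

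Two things are at stake. First, research question 4 asks about four grades, and one of them would have no school-based endline data. Second, a whole grade would be lost on top of ordinary absence, refusal and transfer, and the 20% allowance was not described as covering both. If the outcome that sets the sample size is judged at school, its planned 80% power is exposed.

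**Working it through.** **Calendar**

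| Count from | Plus 10 months | Position |
|---|---|---|
| October 2019 (introduction) | August 2020 | phase 2 cycle |
| October 2020 (section 7) | August 2021 | phase 3 cycle |
| August 2019 launch | June 2020 | inside the phase 1 school year |

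Baseline fieldwork is planned at 12 schools a month, so 30 schools take 30/12 = 2.5 months. If endline takes as long, visits starting on 1 August run to mid-October, 10 to 12.5 months after a 1 October start.

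**The plan's own sample size.** Inputs from section 7.3: 388 for fruit and vegetable consumption, design effect 2, 20% loss, 1000 children at baseline.

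- Analysable children needed: 388 × 2 = 776.
- With 20% loss: 776/0.8 = 970, within about 1% of the stated 980.
- Slack at the proposed baseline: 1000 − 776 = 224.

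**Loss of 6th graders if the outcome is judged at school.** The split by grade is not given; equal grades are assumed.

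- Leavers: 1000/6 = 167, which is 167/224 = 74% of the slack.
- For a 6th-grade share of 14%: 140/224 = 63%. For 20%: 200/224 = 89%.
- Children remaining: 833. Room for other loss: 1 − 776/833 = 6.9%.
- With 20% other loss as well, total loss is 1 − (5/6 × 0.8) = 33%, leaving 667.

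**Power**, taking 388 as giving exactly 80% (two-sided 0.05), with z-sum 1.960 + 0.842 = 2.802:

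- Design effect held at 2: power = Φ(2.802 × √(n/776) − 1.960).
- Intraclass correlation held: ICC = 1/(776/30 − 1) = 0.040; DE = 1 + (n/30 − 1) × 0.040; power = Φ(2.802 × √((n/DE)/388) − 1.960).

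| Scenario | n | DE held at 2 | ICC held |
|---|---|---|---|
| Departure, no other loss | 833 | 82.7% | 81.3% |
| Departure, 5% other loss | 792 | 80.8% | 80.4% |
| Departure, 10% other loss | 750 | 78.6% | 79.3% |
| Departure, 20% other loss | 667 | 73.8% | 77.0% |
| 20% loss, no departure | 800 | 81.2% | 80.6% |

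At 20% ordinary loss the departure costs 81.2 − 73.8 = 7.4 points, or 80.6 − 77.0 = 3.6 points with the ICC held.

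**Sensitivity.** If only the 3rd to 6th grades of research question 4 were sampled, 1000/4 = 250 would leave, more than the 224 slack. The 750 remaining give about 79% before any other loss.

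**The case against.** Four points deserve weight.

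1. **The sizing outcome may not be lost.** Fruit and vegetable consumption is also measured by 24-hour recall, which a traced leaver's caregiver could still give. Only the hypothesis confines the outcome to school; Table 6, the objective and research question 4 do not. This stands, and it makes the 74% and the power figures conditional. A recall from a leaver would, however, describe food eaten at a different school.
2. **The August date is inferred.** Figure 6 is not shown, the protocol says it presents the first stage only, and the plan's month counts are loose: section 7.4 equates about six months after the start with January and April 2020, which are three and six months after October 2019. This stands as a reason for caution. But the study-design text counts from implementation, and the introduction dates that to October.
3. **The effect is modest when ordinary loss is small.** This stands: with the departure alone, power stays above 80%.
4. **Power figures built on 388 are fragile.** This stands too. No baseline proportion is given to check 388, so it is taken at face value.

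A reader might infer that the study will be underpowered, or that 6th graders drop out of every outcome. The documents support neither. The departure fits within the 20% allowance, and the recall, the beverage diary completed at home and all-day accelerometry need tracing rather than attendance at the study school.

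**Conclusion.** The concern holds in a limited form. Following the written rule from either October start puts endline in August, in the next programme cycle. Children in 6th grade at baseline could then give no recess food-weighing data and no study-school PE or recess data.

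The numerical cost applies only if fruit and vegetable consumption is judged at school and grades are equal in size: about 167 children, 74% of the slack (63% to 89% for 6th-grade shares of 14% to 20%). With 20% other loss as well, power is about 74% to 77%, against about 81% without the departure. If the recall is the measure and leavers are traced, that loss does not apply.

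It would be too strong to say that endline is certainly scheduled for August. Figure 6 may show another month, and counting from the August 2019 launch gives June. Even then the text of section 7.3 would need correcting, because as written it leads to the worse date. Confidence is moderate.

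**What to change.** - Replace the ten-month rule in section 7.3 with an endline window that closes before the last day of classes of the school year in which the programme starts. Set it from the official school calendar; the documents give programme phases, not term dates.
- Measure baseline in that same school year. At the planned pace, 2.5 months of visits before 1 October reach back to mid-July, in the preceding August-to-July cycle, so 6th graders measured then could leave before the programme begins, whatever the endline date.
- Reconcile the October 2019 and October 2020 start dates in the introduction, section 2.3 and the opening of section 7.
- If the ten months is kept, restate the expected loss for school-based outcomes (about 33% in total with 20% other loss) and the resulting power. Enrolling more children would not restore endline school data for 6th grade.

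**Cost.** Protocol wording and scheduling; no extra children or visits. Exposure at endline is somewhat shorter: if the window closed at the end of July, the last month of the phase cycle, 2.5 months of visits would fall about 7.5 to 10 months after a 1 October start, and earlier if classes end sooner. Baseline fieldwork is also tighter: if only August and September were available before an October start, 30 schools in two months means 15 a month rather than 12.

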Table 6 presents the sample size necessary for hypotheses testing, considering a significance level of $\alpha = 0.05$, a statistical power of 80%, and a correlation of 0.2 between the basal and final measurements. Considering that the largest sample size required is the one to estimate the effect of the intervention on fruit and vegetable consumption ($n = 388$), a design effect of 2, and 20% losses to follow-up, it is estimated that a total of 980 girls and boys ($n = 490$ per intervention group) are needed.

A baseline measurement of 1000 girls and boys has been proposed. Considering the same assumptions of design effect and loss to follow-up, it was estimated that a sample size of 595 girls and boys is required for accelerometry measurements and the System for Observing Fitness Instruction Time (SOFIT).

Table 6 The sample size required to estimate expected differences

Indicator	Standard deviation	Expected difference	Sample size
Water consumption (ml/day)	631	171	384
MVPA (min/day)	40	10	248
MVPA (min/PE)	9	3.8	248
MVPA (min/recess)	12	3.9	244
Fruit and vegetable consumption (% of schoolchildren)		6.2%	388

Note. MVPA= moderate to vigorous physical activity; PE= physical education.

Schools selection

The intervention group schools will be selected randomly from the predefined list of 58 schools selected by the Ministries of Health and Education to participate in the first phase of implementation of Salud Escolar. The control group will be selected from a list of schools available in Mexico City provided by the Ministry of Education, where the program will not be implemented. Given that the selection of the 58 schools of the intervention group will not be at random, schools from the control group will be as similar as possible to those in the intervention group. Thus, it will be sought that the schools of both groups (i.e, intervention and comparison) are paired based on the following characteristics:

- Location: schools should be in the same geographical area < 5 km.
- Basic Geostatistical Area (BGA): within a similar BGA level
- Type of working day: in the same type of working day (regular, extended or full time)
- Hours: both in the morning or in the afternoon
- Size: schools from both groups will be expected to have a similar number of students and classes.

Participants

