and Practices” (SHPPS) study (Council of Chief State School Officers, no date), from the Health Behavior in School-Aged Children (HBSC) survey (Council of Chief State School Officers, no date), and from the School Health Environment Survey (SHES) (Kroeker *et al.*, 2006). The components of the School Audit Tool assessing the school's built physical environment were taken from the school audit tool of the Sport, Physical activity and Eating behavior: Environmental Determinants in Young people (SPEEDY) study showing acceptable validity and reliability (Jones *et al.*, 2010). The tool also includes items to characterize the school grounds, the aesthetics of the school, the supply of food and access to fast-food restaurants around the school, and the amount of class time spent on physical education (Appendix 16).

Data analysis.

For the baseline evaluation, a descriptive analysis of the sample is contemplated, estimating the means and standard deviations for continuous variables, as well as percentages for categorical variables. Descriptive variables will be estimated in the total sample and by study group. A consistency in the results from the research team and the characteristics of the schools reported in the School Audit Tool will be conducted, using paired t-tests for continuous variables and Chi-square tests for categorical variables. The statistical package Stata 14 will be used for data analysis which will be disaggregated by participants sex and age.

The impact of Salud Escolar will be estimated using a difference in difference analysis considering schools as clustering variables. Behaviors of interest will be the outcome variables and group allocation and time will be the independent variables. The effect of Salud Escolar will be tested by introducing an interaction term between time and group allocation.

Fieldwork

The fieldwork will be carried out by three teams of six members, three supervisors (one for each brigade) and a coordinator. In each team two members will apply accelerometry and anthropometry measurements, four will apply the beverage diary and the 24-hour recall. Each team is estimated to work within each school for approximately one week, which represent a total of 12 schools visited in a month and two and a half months for the full data collection at the baseline stage.

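### The stated 80% power for daily MVPA is not delivered: 595 children give about 33–50%, and Table 6 and its inflation are internally inconsistent.

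*Combined protocol and SAP*

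**What the plan says.** All of this is in section 7.3 of the combined protocol and SAP.

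- Under Study hypothesis, the plan expects that "time engaged in MVPA will increase in total 10 minutes per day" in exposed children relative to the comparison group.
- Under Sample size calculation, Table 6 is said to rest on a significance level of 0.05 and "a statistical power of 80%, and a correlation of 0.2 between the basal and final measurements". Its daily MVPA row (SD, expected difference, sample size) reads "MVPA (min/day) 40 10 248". The row for MVPA per PE class has SD 9, difference 3.8 and again 248.
- The largest entry, 388 for fruit and vegetables, is inflated with "a design effect of 2, and 20% losses to follow-up, it is estimated that a total of 980 girls and boys", which is 490 per group.
- For the accelerometry and SOFIT subsample the text continues "Considering the same assumptions of design effect and loss to follow-up", and "it was estimated that a sample size of 595 girls and boys is required for accelerometry measurements" and SOFIT. The proposed baseline sample is 1,000 children.
- Under Data analysis, "The impact of Salud Escolar will be estimated using a difference in difference analysis considering schools as clustering variables", with the effect tested as a time by group interaction.

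**The concern.** Two things in Table 6 stand out. The same sample size serves two quite different standardised effects: 10/40 = 0.25 SD for daily MVPA and 3.8/9 = 0.42 SD for PE. The 595 also looks small for a 0.25 SD effect once clustering and loss are taken off.

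Daily MVPA is a named impact hypothesis, and the results are meant to inform national scale-up. If the protocol claims 80% power and the study has between a one-in-three and a one-in-two chance of detecting the hypothesised effect, a null result would be read as evidence against the programme when it is not.

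**Working it through.** **Inputs, all from section 7.3.** Alpha 0.05 (taken as two-sided, since sidedness is not stated), power 80%, r = 0.2, design effect 2, loss 20%, two equal arms (15 schools each), and the SDs and differences in Table 6.

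**Formula.** n per arm = 2 × (1.960 + 0.842)² × f × (SD/difference)², with (1.960 + 0.842)² = 7.849. The variance factor f depends on the analysis:
- endline-only, or difference in differences (DiD) if the SD is already that of the change: f = 1
- ANCOVA: f = 1 − 0.2² = 0.96
- DiD with a cross-sectional SD: f = 2(1 − 0.2) = 1.6

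**Step 1: can the 248 for daily MVPA be reproduced?** 2 × 7.849 × (40/10)² = 251.2 per arm for f = 1, 241.1 for f = 0.96 and 401.9 for f = 1.6. So 248 is about right as a per-arm figure for endline-only or ANCOVA. As a total, the requirement is about 502, 482 or 804.

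**Step 2: does one formula fit the table?** Solve for f in each continuous row: f = n / [2 × 7.849 × (SD/difference)²].

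| Row | SD | Difference | n | f if per arm | f if total |
|---|---|---|---|---|---|
| Water | 631 | 171 | 384 | 1.80 | 0.90 |
| MVPA per day | 40 | 10 | 248 | 0.99 | 0.49 |
| MVPA per PE class | 9 | 3.8 | 248 | 2.82 | 1.41 |
| MVPA per recess | 12 | 3.9 | 244 | 1.64 | 0.82 |

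One formula would give one f. The two rows at 248 should differ by (0.422/0.25)² = 2.85-fold. The fruit and vegetable row cannot be checked because no baseline proportion is given.

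**Step 3: the inflation.**
- 248 × 2 × 1.2 = 595.2, which matches 595. Dividing by 0.8 instead gives 620.
- 388 × 2 / 0.8 = 970, close to 980. Multiplying by 1.2 gives 931.

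The two totals therefore do not follow the same loss rule. If the 248 was meant per arm, the factor 2 in 595.2 is the two arms and no design effect has been applied. If it was meant as a total, the factor 2 is the design effect but the 248 is too small to start with.

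**Step 4: what 595 delivers.** Under either reading, 595 × 0.8 / 2 (design effect) / 2 (arms) = 119 effective children per arm, or 238 in all, fewer than the 248. Power = Φ(difference/SE − 1.96), with SE = SD × √(2f/119). For daily MVPA:

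| Analysis | SE (min/day) | Power | Difference detectable at 80% (min/day) | Recruited total for 80% |
|---|---|---|---|---|
| Endline-only, or DiD with change-score SD | 5.19 | 49% | 14.5 | 1,256 |
| ANCOVA | 5.08 | 50% | 14.2 | 1,206 |
| DiD, cross-sectional SD | 6.56 | 33% | 18.4 | 2,009 |

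The last column is 2 × n per arm × 2 / 0.8. A t-based check gives 48% (f = 1) and 33% (f = 1.6).

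In the same order of analyses, recess MVPA has 71/73/51% and PE MVPA 90/91/73%.

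**Step 5: can another reading restore 80%?** Results are again endline-only/ANCOVA/DiD.
- One-sided alpha: 61/63/45%.
- No loss at all: 58/60/40%.
- All 1,000 children wearing accelerometers (1000 × 0.8 / 2 / 2 = 200 per arm): 71/72/51%.
- 595 per arm: 78/80/58%, but this needs 1,190 children, more than the 1,000 proposed.
- No design effect: 78/80/58%, but this contradicts the stated design effect of 2.
- Higher correlation: 80% at 119 per arm needs f = 0.47, that is r of about 0.73 (ANCOVA) or 0.76 (DiD), against the stated 0.2.

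**The case against.** The daily MVPA shortfall itself is not in dispute. The objections are to its lower end, its reach and its weight.

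- *The 33% is conditional.* It needs SD 40 to be cross-sectional, and the plan does not say which SD it is. With a change-score SD the figure is 49%. This stands, so the condition belongs beside the 33%.
- *A design effect of 2 may be too harsh.* If it was meant for about 33 children per school (1,000/30), the implied intraclass correlation is about 0.03. With about 20 per school (595/30) the design effect is about 1.58 and power about 58/60/40%. Differencing may also remove some between-school variation. This is plausible, but the plan says the same design effect applies to the 595, and the alternative still falls well short of 80%.
- *PE and recess are observed by class.* SOFIT follows target students in turn, and nothing says the same children are observed at both times. This stands as a caution: the PE and recess powers are what the plan's child-level inputs imply, not a demonstration that those outcomes are adequately covered.
- *The text shows that entries are totals.* The step from 388 to a total of 980 does point that way, although Table 6 carries no label. Nothing turns on it, because both readings leave 119 per arm.
- *The loss rule is immaterial, and 970 is not 980.* Using 620 instead of 595 moves endline-only power only from 49% to 50%. The point is inconsistency under assumptions said to be the same: multiplying by 1.2 reproduces 595 but misses 980 by 49.
- *The repeated 248 could be a table-reading fault.* Without the PE row, the other three factors (1.80, 0.99, 1.64) still disagree.
- *No primary outcome is named, and fruit and vegetables drive the overall sample.* That is true, but the power claim covers every hypothesis in Table 6, daily MVPA included.

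**Conclusion.** The concern holds. On the plan's own SD, difference, design effect, loss and correlation, power for daily MVPA at 595 children is about 50% (49% endline-only or change-score SD, 50% ANCOVA). It is 33% under the planned difference in differences if SD 40 is cross-sectional. No reading consistent with the documents reaches 80%, and extending accelerometry to all 1,000 children would not reach it either. Table 6 cannot have come from one standard formula, and the two inflated totals do not share a loss rule. The results assume two-sided alpha and equal arms. The 80% statement is wrong as written for a named hypothesis and must be corrected.

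**What to change.** Leave enrolment unchanged and revise the Sample size calculation text in section 7.3:

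1. Recompute Table 6 with one formula that matches the planned group by time analysis (factor 2(1 − r) if the SDs are cross-sectional).
2. State whether entries are totals or per group, whether each SD is cross-sectional or of the change, and whether alpha is two-sided.
3. Apply the design effect and the 20% loss in the same way to the 980 and the 595.
4. Give the baseline proportion behind the fruit and vegetable row, and reconcile its 6.2% with the 6.7% under Study hypothesis.
5. Replace the 80% power statement with the achieved power or detectable difference for each outcome, at the least for daily MVPA.

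The cost is protocol and SAP wording plus a short recalculation. The stated power becomes less favourable, but a null daily MVPA result can then be read for what it is.
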